6.12.2.1. Common Adverse Events

Common TEAEs are those TEAEs that occurred in $\geq 1\%$ before rounding of total ixekizumab treated patients.

The following tables will be provided for common TEAEs by treatment group and study period. When SOC is presented, then events will be ordered by decreasing frequency in the total ixekizumab group, within SOC. When SOC is not presented, then events will be ordered by decreasing frequency in the total ixekizumab group.

The following summaries will be provided for common TEAEs based on the Safety Population for Period 2:

- Common TEAEs by PT nested within SOC
- Common TEAEs by PT
- Common TEAEs by maximum severity by PT nested within SOC.

6.12.3. Deaths, Other Serious Adverse Events, and Other Notable Adverse Events

By-patient listings of deaths, SAEs, and AEs leading to discontinuation will be provided, respectively.

All deaths will be included, regardless of the investigator's or the sponsor's judgment about causality, including:

- any deaths occurring during participation in the study in the database for which data are being presented
- any deaths occurring after a patient leaves (is discontinued from or completed) the study in the database for which data are being presented if the death is:

- the result of a process initiated during the study, regardless of when it actually occurred, or
- occurs during the Period 4 after discontinuation of study drug.

An SAE is any AE that results in one of the following outcomes: death, life-threatening, initial or prolonged hospitalization, disability or permanent damage, congenital anomaly or birth defect, or any other serious/important medical events.

The following summary tables (including treatment group comparison for Period 2) will be provided for the Safety Population for Period 2, and for the Extended Treatment Period Population for Period 3, as well as Combined Periods 2 and 3 for Safety Population who are initially randomized to ixekizumab at Week 0 as well as All Ixekizumab Exposures Safety Population:

- SAEs by PT
- AEs that lead to treatment discontinuation (including death) by PT.

A follow-up emergent serious adverse event (FESAE) is defined as an SAE that first occurred or worsened in severity after the date of Visit 15 (that is, Week 52) or the ETV. The following summary tables will be provided for the Follow-Up Population for Period 4:

- FESAE by PT
- FEAEs that lead to treatment discontinuation (including death) by PT.

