## 4. Study Design

### 4.1. Overview of Study Design

Study IIF-MC-RHBV is a Phase 3, multicenter, randomized, double-blind, active and placebo-controlled, parallel-group, outpatient study examining the efficacy and safety of ixekizumab treatment regimens (80 mg Q2W and 80 mg Q4W SC), as compared to placebo SC in patients with active rad-axSpA who are bDMARD-naive, during a double-blind, 16-week treatment period.

Starting doses of 80 mg and 160 mg (at Week 0) will be evaluated for each ixekizumab regimen. Adalimumab (at the approved dosing regimen of 40 mg SC Q2W) has been selected as the active control for comparison with placebo.

Study RHBV will also evaluate long-term efficacy and safety of ixekizumab during the Extended Treatment Period (Period 3) for a total treatment duration of 1 year (52 weeks). Patients that complete Study RHBV may be eligible to enroll into a long-term study (Study IIF-MC-RHBY [RHBY]) for up to 2 additional years. Patients that do not enroll into Study RHBY will complete the Post-Treatment Follow-Up Period (Period 4) in Study RHBV.

[Figure RHBV.1](#) illustrates the study design, and all treatment groups and administration of the investigational product are described in [Section 6.1](#), and the Study Drug Administration Log is described in [Section 6.2.1](#).

All procedures to be conducted during the study, including timing of all procedures, are indicated in the Schedule of Activities ([Appendix 2](#)). Selected study procedures are to be performed prior to administration of the investigational product, as applicable.

[figure not shown]
For each patient, x-rays and magnetic resonance imaging (MRIs) will be collected according to [Section 8.1.2.20.1](#) and the Schedule of Activities ([Appendix 2](#)). [Appendix 3](#) lists the specific laboratory tests that will be performed for this study.

Patients discontinuing from study treatment who have received at least 1 dose of investigational product will continue to the early termination visit (ETV) prior to proceeding to the Post-Treatment Follow-Up Period. For the management of patient safety, all patients are to be monitored through the Post-Treatment Follow-Up Period at least as frequently as indicated in the Schedule of Activities ([Appendix 2](#)).

Excluded and concomitant medications are detailed in [Section 6.8](#).

Pharmacokinetic (PK) sampling is detailed in [Section 8.5](#).

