## 7. Discontinuation Criteria

The reason for and date of discontinuation from study treatment (investigational product) and reason for and date of discontinuation from study participation will be collected for all randomized patients.

For any patient permanently discontinuing from study treatment, the investigational product will be withheld, and the patient will complete the ETV and the Post-Treatment Follow-Up Period (Period 4), as shown in the Schedule of Activities ([Appendix 2](#)). For patients discontinuing prior to Week 16, the patient will complete additional assessments as described in Section 7.1.1.1 and shown in the Schedule of Activities ([Appendix 2](#)).

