#### **9.5.1. Adverse Events**

Adverse events are classified based upon the Medical Dictionary for Regulatory Activities (MedDRA). A treatment-emergent adverse event (TEAE) is defined as an event that first occurred or worsened in severity after baseline and on or prior to the date of the last visit within the treatment period. Both the date/time of the event onset and the date/time of the first study drug injection are considered when determining TEAEs. Treatment-emergent adverse events will be assigned to the treatment period in which they first occurred or worsened. A follow-up emergent adverse event (FEAE) is defined as an event that first occurred or worsened in severity after the date of Week 52 (Visit 15) or the ETV. For events that are gender specific, the denominator and computation of the percentage will include only patients from the given gender.

An overall summary of AEs will be provided for each of the treatment periods, including the number and percentage of patients who experienced TEAEs, TEAEs by maximum severity, deaths, SAEs, TEAEs related to study drug, discontinuations from the treatment due to an AE, and treatment-emergent AESIs. Treatment-emergent adverse events (all, by maximum severity, and TEAEs possibly related to study drug by the investigator), SAEs including deaths, and AEs that lead to treatment discontinuation will be summarized and analyzed by MedDRA system organ class (SOC) and preferred term.

In addition to general safety parameters, safety information on specific topics of AESIs will also be presented. Potential AESIs will be identified by a standardized MedDRA query (SMQ) or a Lilly defined MedDRA preferred term listing.

Follow-up emergent adverse events, SAEs including deaths, and AEs that lead to study discontinuation will be summarized for Period 4.

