6.8. Treatment Compliance

By-patient listings of randomization schedule for the ITT Population and study drug dispensed (include the CT Lot number) for the Safety Population will be provided.

Throughout treatment periods, randomized patients will record information in a Study Drug Administration Log (captured in the *Exposure as Collected* eCRF page), including the date, time, and anatomical location of administration of investigational product, syringe number, who administered the investigational product, and the reason if the investigational product was not fully administered.

Treatment compliance for each patient per period will be calculated as:

$$\text{Treatment compliance (\%)} = 100 \times \frac{\text{Total number of injections administered}}{\text{Total number of injections prescribed}}$$

- For patients who complete Period 2, the number of injections prescribed (that is, expected) during Period 2 will be equal to 17 (3 injections at Week 0 and 2 injections every 2 weeks from Week 2 to Week 14).
- For patients who discontinue during Period 2, the number of injections prescribed during Period 2 can be derived from the IWRS study drug dispense dataset.
- For patients who complete Period 3, the number of injections prescribed (that is, expected) during Period 3 will be equal to 19 (2 injections at Week 16 and 1 injection every 2 weeks from Week 18 to Week 50).
- For patients who discontinue during Period 3, the number of injections prescribed during Period 3 can be derived from the IWRS study drug dispense dataset.
- The total number of injections administered will be derived using the response to the question "Was dose administered?" on the *Exposure as Collected* eCRF page.

A patient will be considered overall compliant with study treatment within each treatment period if he/she misses no more than 20% of the expected doses, does not miss 2 consecutive doses (all injections at an injection week are counted as 1 dose), and does not over-dose (that is, take more injections at the same time point than specified in the protocol).

Patient treatment compliance by treatment week and overall will be summarized for the Safety Population for Period 2 and for the Extended Treatment Period Population for Period 3. The comparisons between treatment groups during Period 2 will be conducted using Fisher's exact test.

A by-patient listing of study treatment administration and compliance for the Safety Population will be provided.

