6.12.2. Adverse Events

Adverse events (AEs) will be classified based upon the latest version of the MedDRA. Adverse events will be recorded at every study visit. Any condition starting on or after the date of informed consent will be considered an AE. Any preexisting condition which worsens in severity on or after the date of informed consent will be considered and recorded as an AE on the *Adverse Event (AE)* eCRF page from the date of worsening onwards.

A treatment-emergent adverse event (TEAE) is defined as an event that first occurred or worsened in severity after baseline and on or prior to the date of the last visit within the defined treatment period. Both the date/time of the event and the date/time of the dose (that is, injection) are considered when determining TEAEs. Treatment-emergent AEs will be assigned to the study period to which it's considered treatment-emergent:

- The MedDRA lowest level term (LLT) will be used when classifying AEs as treatment-emergent.
- The maximum severity recorded for each LLT prior to the first dose date/time in the treatment Period will be used as the pre-treatment severity for that LLT. If an event during the baseline period has missing severity, and the event persists during the treatment period, then it will be considered as treatment-emergent, regardless of the postbaseline level of severity. Events with a missing severity during the treatment period will be considered treatment-emergent.
- AEs with a particular LLT will be classified as treatment-emergent if they first start on or after the first dose date/time in the treatment period (ie, a patient has no preexisting conditions with that lowest level term), or if the severity is greater than the pre-treatment severity for that lowest level term. If a partial AE start date/time is present, the date/time will be compared as far as possible to the treatment start date/time in order to determine whether the event is treatment-emergent or not. If there is any doubt, the event will be flagged as treatment-emergent.

A follow-up emergent adverse event (FEAE) is defined as an event that first occurred or worsened in severity after the date of Visit 15 (that is, Week 52) or the ETV:

- The MedDRA LLT will be used when classifying AEs as follow-up emergent.
- For AEs that are ongoing at the date of Visit 15 or ETV, the maximum severity recorded for each LLT on or prior to the date of Visit 15 or ETV will be used as the follow-up baseline severity for that LLT.

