If a partial or completely missing AE start date/time or end date/time is present the following imputation rules will be utilized in the analysis:

- For the start date:
 - If year, month, and day are missing, then use the earlier of the patient's first visit date or the consent date.
 - If either month or month and day are missing, then use January 1.
 - If only day is missing, impute the first day of the month.
- For the start time:
 - Impute as 23:59
- For the end date:
 - If year, month, and day are missing, then use the patient's last visit date in the follow-up period.
 - If either month or month and day are missing, then use December 31.
 - If only day is missing, then use the last day of the month.
 - The imputed date will not be beyond the patient's last visit date in the follow-up period.
- For the end time:
 - Impute as 23:59.
- If there is any doubt, the event will be flagged as treatment-emergent or follow-up emergent according the corresponding study period. If a follow-up emergent event was already counted as treatment-emergent during the prior treatment period, it will not be counted as a follow-up emergent event.

Adverse events and TEAEs will be summarized for the following study periods and analysis populations, treatment comparisons between treatment groups in Period 2 will be conducted using a Fisher's exact test:

- Period 2 (Safety Population)
- Period 3 (Extended Treatment Period Population)
- Combined Periods 2 and 3 (Safety Population who are randomized to ixekizumab at Week 0)
- Combined Periods 2 and 3 on ixekizumab treatment only (All Ixekizumab Exposures Safety Population)

The following summaries/analyses will be performed for all the populations above:

- An overall summary of AEs including the number and percentage of patients who experienced TEAE, TEAE by maximum severity, death, SAE, TEAE possibly related to study treatment, discontinuations from the treatment due to an AE, and TEAEs of special interest.

The following summaries will be provided for selective populations above:

- TEAE by system organ class (SOC) and preferred term (PT).
- TEAE by PT.
- TEAE by maximum severity, SOC, and PT.

Follow-up emergent adverse events will be summarized for the Follow-Up Population for Period 4:

- FEAE by PT.

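### The Period 4 table of follow-up emergent adverse events is restricted to treatment discontinuation, which has already happened by then; the protocol asks for study discontinuation

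*SAP*

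**What the plan says.** SAP 6.12.3 names two Period 4 tables for the Follow-Up Population: serious follow-up emergent events by preferred term, and "FEAEs that lead to treatment discontinuation (including death) by PT". SAP 6.12.2 adds a third, all follow-up emergent events by preferred term.

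The window for these events is set in SAP 6.12.2: "A follow-up emergent adverse event (FEAE) is defined as an event that first occurred or worsened in severity after the date of Visit 15", or after the early termination visit (ETV). Protocol 9.5.1 uses the same window.

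Protocol 9.5.1 also states what Period 4 should report: "Follow-up emergent adverse events, SAEs including deaths, and AEs that lead to study discontinuation will be summarized for Period 4". For the treatment periods, the same section speaks of adverse events leading to treatment discontinuation. The protocol therefore keeps the two kinds of discontinuation apart and assigns study discontinuation to Period 4.

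**The concern.** The SAP bullet and the protocol sentence differ in one word, and that word decides whether the table can work. If every patient has stopped investigational product before the follow-up window opens, a table of follow-up emergent events that led to stopping it has almost nothing to hold.

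What is at stake is a safety output that the protocol specifies. Period 4 reporting of adverse events is already brief: the SAP names three tables, and under SAP 6.12.3.1 special-interest summaries are generally not produced for this period, hepatic laboratory tests excepted. A near-empty table with this title, read alone, could suggest that few or no patients had left follow-up because of an adverse event, when it had not asked that question.

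**Working it through.** No arithmetic beyond dates is involved, and the plan gives no figure to reproduce. The check compares when dosing ends with when the follow-up window opens, and then goes through the other Period 4 outputs.

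**1. Patients who complete Week 52.** SAP 6.8 sets the Period 3 injections as 2 at Week 16 and then "1 injection every 2 weeks from Week 18 to Week 50". Protocol Table RHBV.3 agrees. The last scheduled dose comes 52 − 50 = 2 weeks before Visit 15, and the Schedule of Activities dispenses no product at Visit 15. An event that begins or worsens after Visit 15 falls after dosing has ended.

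**2. Patients who stop early.** Protocol 4.1 says that those who discontinue treatment after at least one dose "will continue to the early termination visit (ETV) prior to proceeding to the Post-Treatment Follow-Up Period". Protocol Section 7 gives the same order. The sequence is treatment stop, ETV, Period 4, so an event after the ETV again falls after dosing has ended.

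**3. Patients who enter the long-term study.** Under Protocol 4.1 they do not enter Period 4, so they cannot fill the table.

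**4. Carry-over from treatment.** An event that stopped treatment might worsen after the ETV. SAP 6.12.2 closes most of this route: if a follow-up emergent event "was already counted as treatment-emergent during the prior treatment period, it will not be counted as a follow-up emergent event". One narrow route remains: an event that led to treatment being stopped, was never classed as treatment-emergent, and then worsened after the ETV.

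**5. What can enter the table.** Deaths, through the words in parentheses, and the narrow case in step 4.

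**6. Protocol 9.5.1 against the planned SAP tables.**

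| Period 4 item in Protocol 9.5.1 | SAP table |
|---|---|
| Follow-up emergent events | Yes, by preferred term (6.12.2) |
| Serious events including deaths | Yes, by preferred term (6.12.3) |
| Events leading to study discontinuation | None; the table in this place uses treatment discontinuation (6.12.3) |

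**7. Whether other outputs fill the gap.**
- Disposition (SAP 6.6) counts patients leaving Period 4 by primary reason. It gives a number for adverse event as a reason, but no preferred term.
- The two general tables in step 6 give preferred terms, but do not mark which events led to leaving the study.
- The by-patient listing of adverse events leading to discontinuation (SAP 6.12.3) does not say whether it means treatment, study or both.
- The listings of all adverse events (SAP 6.12.2) and of disposition by period (SAP 6.6) would let a reader match patients to events by hand.

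**The case against.** A reader might infer that non-fatal events leading to study exit go unreported, that patients leaving for this reason are in no Period 4 discontinuation table, or that all such events are lost. The documents do not support any of these. Every non-fatal follow-up emergent event is in the general table by preferred term, and in the serious-event table if serious. A patient whose primary reason for leaving Period 4 is an adverse event is counted in the disposition table. The listings add patient-level detail. A near-empty table would therefore not stand alone as evidence that nobody left.

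It can also be said that the bullet nearly repeats the one given for the treatment periods in the same section, which suggests carried-over wording rather than a decision. In addition, Protocol 9.2 allows changes of method that do not alter a principal feature to be explained in the study report without an amendment. The group affected is small in kind: patients who enter Period 4, have a follow-up emergent event, and leave an off-treatment follow-up because of it.

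All of that stands, and it limits the point to a minor one. It does not remove it. The SAP revision history records no decision to drop the protocol's summary, and programming the bullet as written would not produce it.

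**Conclusion.** The point holds in a limited form. As worded, the table is empty by construction apart from deaths and the narrow case of an event that stopped treatment without being treatment-emergent and later worsened. The Period 4 summary of events leading to study discontinuation, which Protocol 9.5.1 requires, has no table by preferred term. One of the three Period 4 adverse event tables named in the SAP therefore cannot do its work for non-fatal events.

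The size cannot be expressed as a number of patients, because neither document gives a rate of withdrawal from Period 4. What is lost is the link, in a table, between preferred term and study exit; the events and the exits are each reported separately. This is a minor error in the specification of safety reporting. It has no effect on the primary analysis, error control or sample size.

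The conclusion assumes that dosing ends as scheduled before Visit 15 or the ETV, and that the bullet is programmed literally.

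**What to change.** In the Period 4 bullet of SAP 6.12.3, replace treatment with study, keeping deaths and the breakdown by preferred term. In the same section, state whether the by-patient listing of adverse events leading to discontinuation covers treatment discontinuation, study discontinuation or both.

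The cost is two short edits to the SAP and a changed selection rule for one table. No new data on the reason are needed: under Protocol Section 7, "reason for and date of discontinuation from study participation will be collected for all randomized patients", separately from treatment discontinuation. The one thing to confirm is that the case report form ties a study exit for an adverse event to the particular event record, since the documents do not show this and the preferred term depends on it.

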6.12.3.1. Special Safety Topics including Adverse Events of Special Interest

Safety information on special topics including AEs of special interest (AESI) will be presented by treatment group and by study period.

[Table RHBV.6.8](#) provides the definitions/derivations and analyses methods (including analyses, summaries and by-patient listings) of special safety topics including AESIs.

Potential AESIs will be identified by a standardized MedDRA query (SMQ) or a Lilly-defined MedDRA PT listing. Preferred terms within an SMQ will be classified as broad and narrow. In the Lilly-defined MedDRA PT listings, Lilly has provided the broad and narrow classification. The Lilly-defined broad terms are for a more sensitive search of potential events of interest and the Lilly-defined narrow terms are for a more specific search. Therefore, the summaries will include the classifications of broad term (same as pooling narrow and broad terms together) and narrow term.

In the event that the listing of terms or analysis changes for a special safety topic, it will be documented in the program safety analysis plan (PSAP) which will supersede this document; it will not warrant an amendment to the individual study SAP.

Fisher's exact tests will be used to compare the treatment group for the safety population during Period 2.

For Period 3, summaries will be provided for the Extended Treatment Period Population.

For Combined Periods 2 and 3, selective summaries will be provided for the Safety Population who are initially randomized to Ixekizumab at Week 0.

In addition, for Combined Periods 2 and 3 on ixekizumab treatment only, selective summaries will be provided for the All Ixekizumab Exposures Safety Population.

In general, AESI summary will not be provided for Follow-Up Population during Period 4 except hepatic laboratory tests.

Table RHBV.6.8. Definitions and Analyses of Special Safety Topics including Adverse Events of Special Interest

Special Safety Topic	Definition / Derivation	Analysis / Summary / Listing
Hepatic	
Hepatic AE analysis will include events that are potentially drug-related hepatic disorders by using the Medical Dictionary for Regulatory Activities (MedDRA) PTs contained in any of the following standardized MedDRA query (SMQ) or sub-SMQ as defined in MedDRA:
 
 • Broad and narrow terms in the Liver related investigations, signs and symptoms (20000008) • Broad and narrow terms in the Cholestasis and jaundice of hepatic origin (20000009) • Broad and narrow terms in the Hepatitis, non-infectious (20000010) • Broad and narrow terms in the Hepatic failure, fibrosis and cirrhosis and other liver damage (20000013) • Narrow terms in the Liver-related coagulation and bleeding disturbances (20000015) 	
Period 2 (Fisher’s exact test), Period 3 (Summary), Combined Periods 2 and 3 (Summary): TEAE by PT within SMQ or sub-SMQ. Listing: TEAE (included in the same listing with cytopenia, depression and interstitial lung disease AESIs)

	
Elevations in hepatic laboratory tests (ALT, AST, ALP, total bilirubin) using Performing Lab Reference Ranges are defined as:
 
 • Include scheduled visits, unscheduled visits, and repeat measurements. • Alanine aminotransferase (ALT) or aspartate aminotransferase (AST): maximum postbaseline measurement ≥ 3 times ($3\times$), 5 times ($5\times$), 10 times ($10\times$), and 20 times ($20\times$) the Performing Lab upper limit of normal (ULN) for all patients with a postbaseline value. 
 ○ The analysis of $3\times$ ULN will contain 4 subsets: patients whose non-missing maximum baseline value is $\leq 1\times$ ULN, $>1\times$ ULN to $<3\times$ ULN, $\geq 3\times$ ULN, or missing. ○ The analysis of $5\times$ ULN will contain 5 subsets: patients whose non-missing maximum baseline value is $\leq 1\times$ ULN, $>1\times$ ULN to $<3\times$ ULN, $\geq 3\times$ ULN to $<5\times$ ULN, $\geq 5\times$ ULN, or missing. ○ The analysis of $10\times$ ULN will contain 6 subsets: patients whose non-missing maximum baseline value is $\leq 1\times$ ULN, $>1\times$ ULN to $<3\times$ ULN, $\geq 3\times$ ULN to $<5\times$ ULN, $\geq 5\times$ ULN to $<10\times$ ULN, $\geq 10\times$ ULN, or missing. ○ The analysis of $20\times$ ULN will contain 7 subsets: patients whose non-missing maximum baseline value is $\leq 1\times$ ULN, $>1\times$ ULN to $<3\times$ ULN, $\geq 3\times$ ULN to $<5\times$ ULN, $\geq 5\times$ ULN to $<10\times$ ULN, $\geq 10\times$ ULN to $<20\times$ ULN, $\geq 20\times$ ULN, or missing. • Total bilirubin: maximum postbaseline measurement ≥ 1.5 times ($1.5\times$), and ≥ 2 times ($2\times$) the Performing Lab ULN for all patients with a postbaseline value 
 ○ The analysis of $1.5\times$ ULN will contain 4 subsets: patients whose non-missing maximum baseline value is $\leq 1\times$ ULN, $>1\times$ ULN to $<1.5\times$ ULN, $\geq 1.5\times$ ULN, or missing. ○ The analysis of $2\times$ ULN will contain 5 subsets: patients whose non-missing maximum baseline 	
Period 2 (Fisher’s exact test), and Period 3 (Summary): Elevations in hepatic laboratory tests: maximum baseline category to abnormal maximum postbaseline category

Special Safety Topic	Definition / Derivation	Analysis / Summary / Listing
	
value is $\leq 1 \times \text{ULN}$, $> 1 \times \text{ULN}$ to $< 1.5 \times \text{ULN}$, $\geq 1.5 \times \text{ULN}$ to $< 2 \times \text{ULN}$, $\geq 2 \times \text{ULN}$, or missing.
 
 ALP: maximum postbaseline measurement > 1.5 times ($1.5 \times$) the Performing Lab ULN for all patients with a postbaseline value, and divided into 4 subsets: patients whose non-missing maximum baseline value is $\leq 1 \times \text{ULN}$, $> 1 \times \text{ULN}$ to $\leq 1.5 \times \text{ULN}$, $> 1.5 \times \text{ULN}$, or missing. 	
	
Shift for ALT, AST, ALP and total bilirubin from maximum baseline to maximum postbaseline will be produced with the requirements using Performing Lab Reference Ranges:
 
 Include scheduled visits, unscheduled visits, and repeat measurements. Use the maximum non-missing value in the baseline period. Use the maximum non-missing postbaseline value within each study period. Categories are: 
 ALT: $\leq 1 \times \text{ULN}$, > 1 to $< 3 \times \text{ULN}$, ≥ 3 to $< 5 \times \text{ULN}$, ≥ 5 to $< 10 \times \text{ULN}$, ≥ 10 to $< 20 \times \text{ULN}$, and $\geq 20 \times \text{ULN}$ AST: $\leq 1 \times \text{ULN}$, > 1 to $< 3 \times \text{ULN}$, ≥ 3 to $< 5 \times \text{ULN}$, ≥ 5 to $< 10 \times \text{ULN}$, ≥ 10 to $< 20 \times \text{ULN}$ and $\geq 20 \times \text{ULN}$ Total bilirubin: $\leq 1 \times \text{ULN}$, > 1 to $< 1.5 \times \text{ULN}$, ≥ 1.5 to $< 2 \times \text{ULN}$, $\geq 2 \times \text{ULN}$ ALP: $\leq 1 \times \text{ULN}$, > 1 to $\leq 1.5 \times \text{ULN}$, $> 1.5 \times \text{ULN}$ With additional categories: 
 Decreased: postbaseline category $<$ baseline category Increased: postbaseline category $>$ baseline category Same: postbaseline category = baseline category 	
Period 2, Period 3 (Summary), Combined Periods 2 and 3 (Summary): Shifts from maximum baseline to maximum postbaseline category

	
Elevated hepatic criteria: maximum ALT $\geq 3 \times \text{ULN}$ and maximum total bilirubin $\geq 2 \times \text{ULN}$ using Performing Lab Reference Ranges. Listing of patients who meet any of the following criteria:
 
 Elevated hepatic criteria: defined as maximum ALT $\geq 3 \times \text{ULN}$ and maximum total bilirubin $\geq 2 \times \text{ULN}$ An ALT or AST $\geq 3 \times \text{ULN}$ An alkaline phosphatase (ALP) $> 1.5 \times \text{ULN}$ A total bilirubin $\geq 2 \times \text{ULN}$ 
The listing will include: patient demographics, concomitant medications, ALT/AST/ALP/total bilirubin/GGT by visit, treatment start and stop dates, and reason for treatment discontinuation.
	
Period 2 (Fisher’s exact test), Period 3, and Period 4 (Summary): Elevated hepatic criteria
 
Listing: Elevations in hepatic laboratory tests

	
Evaluation of Drug-Induced Serious Hepatotoxicity (eDISH) plot: use maximum ALT measurement and maximum total bilirubin measurement with patients having at least one postbaseline ALT and total bilirubin, which contributes one point to the plot. The measurements do not need to be taken at the
	
Period 2: eDISH plot (to be prepared in Spotfire)

Special Safety Topic	Definition / Derivation	Analysis / Summary / Listing
	same blood draw.	
Cytopenias	
Cytopenias are defined using the PTs from the following 2 sub-SMQs of the Haematopoietic cytopenias SMQ (20000027) as specified in MedDRA:
 
 • Broad and narrow terms in the Haematopoietic leukopenia (20000030) • Broad and narrow terms in the Haematopoietic thrombocytopenia (20000031) 	
Period 2 (Fisher’s exact test) and Period 3 (Summary): Combined Periods 2 and 3 (Summary): TEAE by PT within sub-SMQ Listing: TEAE (included in the same listing with hepatic, depression and interstitial lung disease AESIs)

Infections	
Infections are events including all infections (defined using all the MedDRA PTs from the Infections and infestations OSC), serious infections, potential opportunistic infections, and infections resulting in anti-infective medication administration (i.e. antibacterial, antivirals, antifungals, antiparasitic treatments).
	
Period 2 (Fisher’s exact test), Period 3 (Summary), Combined Periods 2 and 3 (Summary): SAE by PT

	
Anti-infective medications are defined in Appendix 7. Listing of patients experiencing a TEAE of infections will be provided including the following additional information: anti-infective medications use (if treated) with medication start/end dates, indication for use, and route; minimum postbaseline value within treatment Period 2 for leukocytes, platelets, lymphocytes, and absolute neutrophils.
	
Listing: TEAE with anti-infective medications.

	
The list of MedDRA terms used to identify infections that are predefined as potential OIs are found in Appendix 11. This list contains PTs as contained within categories (narrow or broad) from the Infections and infestations SOC and the Investigations SOC which can assist in identifying potential OIs. The narrow terms are considered OIs unless medical review determines that the reported term is not consistent with the patient’s clinical history/presentation/course. Medical review of broad terms is needed for final determination of patients meeting the program definition of OIs. Listing of patients experiencing a TEAE of OIs will be provided including the following additional information: source of identification (CRF or Lilly specified list), primary/secondary site of infection, primary/secondary infection type, primary/secondary identified by a laboratory diagnostic test (Yes/No), acquired in a Health care setting (Yes/No).
	
Period 2 TEAE of OIs by PT TEAE of OIs by maximum severity by PT Period 3 and Combined Periods 2 and 3 (Summary): TEAE of OIs by maximum severity by PT Listing: TEAE of OIs

	
The duration of each common ($\geq 1\%$ of total ixekizumab) TEAE PT of Infections, and duration of narrow terms for Opportunistic infections are defined as:
	
Period 2 (Summary): Duration of Common TEAE –

Special Safety Topic	Definition / Derivation	Analysis / Summary / Listing
	
Duration of treatment-emergent AE Infections (in weeks) = (End date of AE – Start date of AE + 1) / 7
 
Only TEAEs of infections beginning during treatment Period 2 or Period 3 will be included in the summary. If an AE has not ended by the date of completion of the treatment periods 2 or 3, or date of early discontinuation, it will be censored as of that date (last visit within the treatment period 2 or treatment period 3, or date of early discontinuation). If a patient has multiple episodes of the same TEAE, the episode with the greatest severity will be used for the duration of event calculation. If a patient has multiple episodes of the same TEAE with the same severity, the episode with the longest duration will be used for the duration of event calculation.
	
Infections


Allergic Reactions/Hypersensitivities
	
Allergic reactions/hypersensitivity events will be categorized as either anaphylaxis or non-anaphylaxis events (these will refer to events that are not localized to the site of injection) and summarized separately.
 
Allergic Reactions/Hypersensitivity Events, Anaphylaxis: Anaphylaxis has been broadly defined as “a serious allergic reaction that is rapid in onset and may cause death” (Sampson et al. 2006).
 
Identification of cases of potential anaphylaxis from the clinical trial data involves two criteria:
 
 1) designed to specifically identify cases (following Criterion 1) based on narrow terms from the MedDRA SMQ for anaphylactic reaction (20000021). Criterion 1 for anaphylaxis is defined by the presence of a TEAE based on the following MedDRA PTs from the anaphylactic reaction SMQ: 
 • Anaphylactic reaction • Anaphylactic shock • Anaphylactoid reaction • Anaphylactoid shock • Kounis Syndrome • Type 1 hypersensitivity 2) to identify possible cases, following Criterion 2 as defined by Sampson et al. (2006). Criterion 2 for anaphylaxis requires having TEAEs from two or more of four categories of AEs as described by Sampson et al. (2006). Occurrence of these events should be nearly coincident; based on recording of events on CRFs. All qualifying event must be within 1 day of study drug injection. 
The 4 categories to be considered in Criterion 2 are:
 
 • Category A: Involvement of the skin-mucosal tissue • Category B: Respiratory compromise • Category C: Reduced blood pressure or associated symptoms • Category D: Persistent gastrointestinal symptoms 
The specific MedDRA PTs covered by each of these Criterion 2 categories are shown in
	
Period 2 (Fisher’s exact test), and Period 3 (Summary): TEAE by maximum severity by PT within Category, SAE by PT within Category, Combined Periods 2 and 3 (Summary): SAE by PT within Category TEAE by maximum severity by PT within Category

Special Safety Topic	Definition / Derivation	Analysis / Summary / Listing
	
Appendix 8.
 
Summaries of Criterion 2 anaphylactic TEAEs will be provided by the specific combination of categories as follows:
 
 • AB: events based on meeting Category A and Category B (but no other category) • AC: events based on meeting Category A and Category C (but no other category) • AD: events based on meeting Category A and Category D (but no other category) • BC: events based on meeting Category B and Category C (but no other category) • BD: events based on meeting Category B and Category D (but no other category) • CD: events based on meeting Category C and Category D (but no other category) • ABC: events based on meeting Category A, Category B and Category C (but no other category) • ABD: events based on meeting Category A, Category B and Category D (but no other category) • ACD: events based on meeting Category A, Category C and Category D (but no other category) • BCD: events based on meeting Category B, Category C and Category D (but no other category) • ABCD: events based on meeting each of the 4 Criterion 2 categories. 
Summaries of treatment-emergent anaphylactic AEs will be provided for patients meeting each of the 2 criteria and for patients who meet either criteria overall. Severity of treatment-emergent Criterion 2 anaphylactic AEs will be based on the maximum severity of the specific events met by the patient. Maximum severity of an (or overall) treatment-emergent anaphylactic AE will be based on the maximum severity within Criterion 1 and/or Criterion 2.
 
Allergic Reactions/Hypersensitivity Events, Non-Anaphylaxis: TEAEs of allergic reaction/hypersensitivity categorized as non-anaphylaxis events are defined by the narrow terms within Hypersensitivity SMQ (20000214) excluding the PTs noted in Appendix 9 and excluding the anaphylactic events as defined above.
 
A by-patient listing will be provided for all patients experiencing TEAE of allergic reactions/hypersensitivities at any time, including status/criterion of anaphylaxis or non-anaphylaxis, and the associated information collected on Allergic / Hypersensitivity Reaction Follow-Up eCRF page if identified by the investigator.
	
Injection Site	Injection site reaction is defined using the PTs from the MedDRA HLT of Injection site reactions as	
Listing: TEAE including information collected on Allergic / Hypersensitivity Reaction Follow-Up eCRF page
 
Period 2 (Fisher’s exact test) and

